**c) Proposed Start Date (may not precede IRB approval date):**

August 1, 2015

2.

Study Procedures (If this is a student project, the methods section of the thesis or dissertation proposal must be attached in section #16 - Attachment section.)

**a) In lay language, describe all the procedures, from screening through end-of-study, that the human subject must undergo in the research project, including study visits, drug treatments, randomization and the procedures that are part of standard of care. Please note: Do NOT respond "See Attachment Section." If you would like to add tables, charts, etc., attach those files in the Attachment section (#16).**

Study Overview:

Pre-diabetic and healthy participants will first undergo a medical questionnaire, resting ECG, graded exercise test with ECG and assessment of VO2max, anthropometric measurement (height, weight and body composition by DEXA scanning), an oral glucose tolerance test (OGTT), and a muscle biopsy.

Prediabetic participants will be screened to eliminate those lactose intolerant, medications known to affect the primary outcomes, medications or recent procedures contraindicated with metformin or not pre-diabetic. Subjects who meet these criteria will be randomized so that subject characteristics are matched between groups, while the study team and participants will remain blinded to treatment (i.e., randomized, double-blind study design). Subjects will be assigned to exercise + carbohydrate + placebo, exercise + protein + placebo, exercise + carbohydrate + metformin, or exercise + protein + metformin.

A minimum of two days apart from the VO2max test, skeletal muscle will be sampled from pre-diabetic and healthy participants. During these visits, pre-diabetic subjects will have the option to participate in a study to test the impact of one counseling session on physical activity after completion of the exercise training and to identify individual, socio-cultural and environmental determinants of physical activity 12 weeks after the end of the exercise intervention. If the subjects wish to participate they will complete questionnaires to measure sociodemographic information, physical activity, self-efficacy, planning, self-regulation and outcome expectancy of exercise, and perceptions of neighborhood support at baseline, completion of exercise training and 12 weeks after the exercise training.

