Pre diabetic and healthy participants will also have the option to participate in a study to wear a Dexcom generation 6 (G6) continuous glucose monitor (CGM) to measure glucose values every 5 minutes. Healthy participants will wear the device once for up to 10 consecutive days. Pre-diabetic participants will wear the device for up to 10-consecutive days at three different time points: before, during and after the 12-week exercise intervention for a total of 30 days wearing the CGM. The Dexcom G6 CGM is for investigational use only and is not FDA approved. The G6 is modeled after commercially available, FDA approved CGM devices. The differences between the G6 and commercially available devices are a reduced calibration scheme, meaning less finger stick blood glucose measurements for calibration; a longer wear for up to 10 days for the G6 vs. 7 days for commercially available product. Last, commercially available devices could give false high glucose readings if individuals took acetaminophen. The G6 sensor contains updated sensor technology aimed to block the interference of acetaminophen.

After randomization into placebo or metformin groups, the pre-diabetic subjects will begin a 12-wk exercise

intervention consisting of 3 days per week of aerobic exercise training with post-exercise consumption of a 20 gram protein beverage or isocaloric carbohydrate beverage. We have completed this supplementation protocol in previous studies and a currently ongoing investigation.

At the 8-wk time point, pre-diabetic subjects will begin the daily consumption of heavy water (D2O) for the assessment of mitochondrial and individual protein synthesis. At the completion of the training period, the pre-diabetic subjects will repeat all assessments performed prior to training including the DEXA, VO2max, OGTT and muscle sample. Muscle samples obtained pre- and post-training will be used to evaluate mitochondrial function using high-resolution respirometry, western blot analysis, and stable isotope incorporation (post only).

Healthy participants will complete the medical history questionnaire, resting ECG, graded exercise testing (ECG and VO2max), DEXA, OGTT, CGM, and muscle biopsy.

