**3. Background**

**a) Describe past experimental and/or clinical findings leading to the formulation of the study, if applicable.**

Physical activity and the biguanide drug Metformin have been shown independently to reduce the incidence of T2D. Interestingly, these data also suggest in adults over the age of 60 metformin had marginal efficacy while physical activity lowered incidence of T2D by 70%. Currently, governing agencies recommend physical activity and metformin together for individuals with pre-diabetes of all ages to prevent the progression to overt T2D. Until recently, the interaction between exercise and metformin has been largely understudied. Members of our investigative team have previously showed that metformin does not enhance but may blunt the glucoregulatory and cardiovascular response to acute and chronic exercise, which is especially relevant to older adults. A purported mechanism of action is that metformin inhibits mitochondrial respiration, which likely limits VO2max and mitochondrial protein synthesis. We have previously demonstrated that post-aerobic exercise dairy feeding can improve VO2max to a greater extent than post-exercise carbohydrate beverage. Therefore, we feel dairy supplementation may override the potential inhibition of metformin on exercise adaptations and maximize the benefits for older adults. To date, real-time continuous glucose monitoring is limited in individuals at risk of T2D. Moreover, glucose profiles via CGM during or in response to exercise, metformin and/or post-exercise nutrition have yet to be fully characterized. Much clinical research is limited to measurements in the clinical research setting while real-time glucose monitoring performed in both the standardized clinical research setting and in free-living scenarios is novelty of the current study design that will close a gap in knowledge regarding glucoregulatory effects of exercise, metformin and/or standardized post-exercise nutrition.

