**\*\*\* Subject Population (a-g) \*\*\***

8. Subject Population - In the space below, please detail the participants that you are requesting to recruit (include requested participant number and description of each group requested). (Input N/A if not applicable)
- a) **Requested Participant Description (Include number of participants that you plan to study and description of each group requested, if applicable).**

We plan to recruit 120 men and women with an estimation that 15-25% of participants will not qualify (i.e., screen out) and 15-25% of participants will not complete the study (i.e. drop out). We plan to complete the study in 60 men and women aged >55 years who are prediabetic defined as impaired fasting glucose (100 to 126 mg/dl), HbA1c (5.7-6.4%), family history of type 2 diabetes, and/or impaired glucose tolerance defined as 2 hour postprandial blood glucose of 140 to 200 mg/dl. Participants will be eligible if they meet any 1 of these criteria.

10 healthy individuals, 18-45 years old who have normal glucose values (fasting glucose (<100mg/dl), HbA1c (<5.7%), 2 hour postprandial blood glucose (<140mg/dl)) or no family history of type 2 diabetes will be recruited.

Sub-study: 20 pre diabetic participants and 10 healthy individuals will complete the study.  
Subpopulation of [xx] participants will be recruited for Physical Activity Behavior Counseling (previously approved in Amendment 3.

- b) **What is the rationale for studying the requested group(s) of participants?**

Individuals at risk for T2D are the intended population for metformin; CGM; and Counseling studies. We will use a healthy control group to compare to individuals at risk for T2D.

- c) **If applicable, state the rationale for involvement of potentially vulnerable subjects to be entered into the study, including minors, pregnant women, economically and educationally disadvantaged, or decisionally impaired subjects. Specify the measures being taken to minimize the risks and the chance of harm to the potentially vulnerable subjects.**

We will not enroll minors, pregnant women, economically and educationally disadvantaged, or decisionally impaired subjects.

- d) **If women, minorities, or minors are not included, a clear compelling rationale must be provided. Examples for not including minors: disease does not occur in children; drug or device would interfere with normal growth and development; etc.**

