**Statistical Plan**

Data are presented as mean  $\pm$  standard error of the mean (SEM) and a significance was set a priori at  $P < 0.05$ . Normality was confirmed by the D'Agostino and Pearson test. A two-way ANOVA (Treatment Group x Time) with repeated measures for time was performed. Upon a significant effect, a Holm-Sidak's post-hoc test was used for multiple comparisons. When comparing the change ( $\Delta$ ) from pre to post-intervention between groups, data were analyzed using an unpaired t-test. Pearson's correlation coefficient ( $r$ ) was used to determine associations between dependent variables. GraphPad Prism 7.0 was used to perform statistical analysis

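### The planned Pearson correlations take no account of the four randomised arms, so if arms are pooled, shared treatment effects can create, inflate or mask an association

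*Combined protocol and SAP*

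**What the plan says.** The Statistical Plan gives correlation one sentence: Pearson's r "was used to determine associations between dependent variables". It does not name the variable pairs, the arms included, the time point or any adjustment. Treatment group and time appear only in the repeated-measures ANOVA sentence. Pre-to-post change appears only in the unpaired t-test sentence. The significance level is 0.05; sidedness is not stated.

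The design around that sentence is as follows.

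- Section 2a (Study Overview) randomises prediabetic participants to "exercise + carbohydrate + placebo, exercise + protein + placebo, exercise + carbohydrate + metformin, or exercise + protein + metformin".
- Section 8a states the target: "We plan to complete the study in 60 men and women aged >55 years".
- Section 2a also says: "Muscle samples obtained pre- and post-training will be used to evaluate mitochondrial function". DEXA, VO2max and the OGTT are repeated after training as well. Isotope incorporation is the exception, because it is measured after training only.
- Section 3a (Background) gives the rationale that "metformin inhibits mitochondrial respiration, which likely limits VO2max and mitochondrial protein synthesis". It adds that dairy feeding after aerobic exercise has improved VO2max more than a carbohydrate drink. Section 1a proposes that milk protein enhances the mitochondrial protein synthesis response.

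**The concern.** A plain Pearson r treats all its points as one homogeneous sample. In this trial the points can come from four arms that were chosen because they should move the outcomes. When two outcomes are both shifted by treatment, the arm means line up. A pooled r then picks up that alignment even if, within every arm, a participant's value on one outcome says nothing about the other. When treatment shifts the two outcomes in opposite directions, a real within-arm association can be hidden.

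What is at stake is interpretation. A significant correlation between, say, respiration and VO2max could be taken as support for the metformin mechanism in Section 3a when it only restates the treatment effect on each outcome. These are secondary analyses, so the randomised comparisons do not depend on them.

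**Working it through.** The documents contain no correlation, power or effect-size figure, so there is nothing of the plan's own to reproduce.

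**Inputs from the documents.** Four arms in a 2×2 layout (Section 2a), 60 completers (Section 8a), alpha 0.05 (Statistical Plan).

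**Assumptions.** Equal allocation (15 per arm), two-sided tests, normal data, the same arm shift on both outcomes, and a true within-arm correlation of 0. Effect sizes are shown as a range.

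**Step 1: threshold.** For n = 60, the critical |r| = t/√(58 + t²) with t = 2.002, which is 0.254. Within a single arm of 15 it is 0.514.

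**Step 2: induced correlation.** Let V be the variance of the arm means in within-arm SD units. If both outcomes carry the same arm shifts, the expected pooled r = V/(1 + V).

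- Metformin alone, shift d: V = d²/4. At d = 0.5, V = 0.0625 and r = 0.059. At d = 1.0, V = 0.25 and r = 0.20.
- Metformin −d and protein +d: V = d²/2. At d = 0.5, V = 0.125 and r = 0.111. At d = 1.0, V = 0.5 and r = 0.333.

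**Step 3: false positives** (40,000 simulated trials per row; plain r on 58 df, partial r given the four arms on 55 df).

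| Shared effect | d (SD) | Mean pooled r | Plain r significant | Arm-adjusted significant |
|---|---|---|---|---|
| None | 0 | 0.00 | 5.1% | 5.1% |
| Metformin only | 0.25 | 0.015 | 5.2% | 5.1% |
| Metformin only | 0.5 | 0.059 | 7.2% | 4.8% |
| Metformin only | 0.8 | 0.139 | 18.3% | 5.1% |
| Metformin only | 1.0 | 0.202 | 34.0% | 5.0% |
| Metformin and protein | 0.25 | 0.030 | 5.7% | 5.2% |
| Metformin and protein | 0.5 | 0.112 | 13.6% | 5.0% |
| Metformin and protein | 0.8 | 0.244 | 47.9% | 5.1% |
| Metformin and protein | 1.0 | 0.337 | 78.2% | 5.0% |

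**Step 4: masking.** Take a true within-arm r of 0.40 and metformin effects of 0.8 SD in opposite directions. The expected pooled r is (0.40 − 0.16)/(1 + 0.16) = 0.21; the simulation gave 0.20.

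**Step 5: training effect common to all arms.** This adds a constant to every post value. It cannot change r for change scores or post-only values: the simulated false-positive rate was 4.8% to 5.3% throughout. It matters only if pre and post rows are stacked as 120 points. With a pre-post correlation of 0.5, stacking gives 7.9% with no training shift (from counting each person twice), 12.2% at 0.5 SD, 34.3% at 0.8 SD and 61.1% at 1.0 SD. Arm adjustment would not remove this; using one value per participant does.

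**The case against.** The strongest objection is that the sentence is silent rather than wrong. It does not say that arms are pooled or that pre and post rows are stacked. Correlations within an arm, at baseline or on change scores all fit the wording. That stands, and it limits the point to what can happen if arms are pooled.

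A reader might infer that any correlation run under this plan has an invalid p-value. The documents do not support that. Baseline values precede any arm effect, and a within-arm r contains none, so plain Pearson is sound for both. A reader might also infer that the training effect itself will generate correlations. Step 5 shows that this needs stacked rows, which the plan does not describe.

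It is also fair to say that the larger percentages depend on effect sizes the documents do not give, and that the highest require both factors to act equally on both outcomes. For a metformin-only effect of 0.5 SD or less, the inflation is small. Finally, a pooled r is a legitimate description of the mixed sample, and the plan speaks of associations, not mechanism.

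What survives is narrower. Pooling is compatible with the text and is a natural use of 60 participants, since a within-arm r has about 15 points and needs |r| above 0.51. The protocol's own rationale predicts the shared arm effects that make a pooled r hard to interpret. Leaving the choice open until the data are seen is avoidable.

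**Conclusion.** The concern holds as a modest, inexpensive improvement. The plan states an unadjusted Pearson r in a trial whose own background expects several outcomes to shift together by arm. If arms are pooled, shared arm effects can create, inflate or mask r.

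Under the stated assumptions (60 completers, 15 per arm, two-sided 0.05, equal shifts on both outcomes, no within-arm association), false positives run from about 7% at 0.5 SD to 34% at 1.0 SD for a metformin-only effect. They run from 14% to 78% over the same range when both factors act. Arm adjustment holds the rate at about 5% in every case. The documents do not establish which of these effect sizes applies, nor that pooling is intended.

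**What to change.** Replace the correlation sentence in the Statistical Plan with wording to this effect:

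- Each participant contributes one value per outcome: the pre-to-post change, or the post-training value for outcomes measured only then, such as isotope incorporation. Pre and post rows are not stacked.
- Report the partial correlation adjusted for the two randomised factors (drink and drug) and their interaction, with its 95% CI.
- Name the variable pairs, and label the analyses exploratory.

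The cost is 3 degrees of freedom, from 60 − 2 = 58 to 55. The critical |r| rises from 0.254 to 2.004/√(55 + 2.004²) = 0.261. No new data are needed and the randomised comparisons do not change.
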